8.3 Definitions

Adverse Event

An adverse event (AE) is any untoward medical occurrence in a patient receiving study treatment and which does not necessarily have a causal relationship with this treatment. An AE can be any unfavorable and unintended sign (including an abnormal laboratory finding), symptom, or disease temporally associated with the use of an experimental intervention, whether or not related to the intervention.

- *Diagnostic and therapeutic non-invasive and invasive (i.e., surgical) procedures will not be reported as adverse events. However, the medical condition for which the procedure was performed must be reported if it meets the definition of an adverse event unless it is a pre-existing (prior to protocol treatment) condition.*

- *Abnormal laboratory values or test results constitute adverse events if they induce clinical signs or symptoms or require therapy. They are to be captured under the signs, symptoms or diagnoses associated with them.*

Serious Adverse Event

An adverse event is considered “serious” if, in the view of either the investigator, it results in any of the following outcomes:

- Death
If death results from (progression of) the disease, the disease should be reported as event (SAE) itself.
- A life-threatening adverse event
An adverse even is considered ‘life-threatening’ if, in the view of either the investigator [or sponsor], its occurrence places the patient or subject at immediate risk of death. It does not include an adverse event that, had it occurred in a more severe form, might have caused death.
- Inpatient hospitalization or prolongation of existing hospitalization for ≥ 24 hours.
- A persistent or significant incapacity or substantial disruption of the ability to conduct normal life functions
- A congenital anomaly/birth defect
- Important medical event
Any event that may not result in death, be life-threatening, or require hospitalization may be considered serious when, based upon appropriate medical judgment, they may jeopardize the patient and may require medical or surgical intervention to prevent one of the outcomes listed in this definition of “Serious Adverse Event”. Examples of such medical events include allergic bronchospasm requiring intensive treatment in an emergency room or at home; convulsions that do not result in inpatient hospitalization or the development of drug dependency or drug abuse.

Previously planned (prior to signing the informed consent form) surgeries should not be reported as SAEs unless the underlying medical condition has worsened during the course of the study. Preplanned hospitalizations or procedures for preexisting conditions that are already recorded in the patient’s medical history at the time of study enrollment should not be considered SAEs. Hospitalization or prolongation of hospitalization without a precipitating clinical AE (for example, for the administration of study therapy or other protocol-required procedure) should not be considered SAEs. However, if the preexisting condition worsened during the course of the study, it should be reported as an SAE.

Expected Adverse Events

An adverse event (AE) is considered “expected” if:

- For approved and marketed drugs or devices, those adverse events are described in the approved Package Insert (Label).
- For investigational new drugs or devices, those adverse events are described in the FDA Investigator’s Brochure.

- In clinical research studies, information on expected adverse events is also summarized in the protocol and in the consent document. See section 9.1 for the list of expected adverse events related to the drug under study.

Unexpected Adverse Event

An adverse event (AE) is considered “unexpected” if it is not described in the Package Insert, Investigator’s Brochure, in the protocol, or in the informed consent document.

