5.2 Toxities and Dosing Delays/Dose Modifications

Any patient who receives treatment on this protocol will be evaluable for toxicity. Each patient will be assessed for the development of toxicity according to the Time and Events Table (Section 6.1). Toxicity will be assessed according to the NCI Common Terminology Criteria for Adverse Events (CTCAE), version 4.03. Dose changes of either study drug is NOT permitted. Doses can be held however as necessary. Dosing holds should be made according to the system showing the greatest degree of toxicity.

Adverse Event Related vs Unrelated Dose Delays: If dose delay is due to an unrelated Adverse Event then reason for hold must be documented. Any patient on this protocol will be allowed to continue to receive study treatment at the investigator's discretion, regardless of AE relatedness. Do not have to delay dose for unrelated Adverse Event.

5.2.1 Treatment delay for toxicity of more than 84 days from last intended therapy will result in treatment discontinuation for the specific drug(s) responsible for the toxicity. If ipilimumab is permanently discontinued, then discontinue Nivolumab 3mg/kg. Nivolumab 480 mg can be continued.

5.2.2 Investigators should consider dose re-calculation of ipilimumab with change in weight as per standard of care/institutional guidelines. However, a change in weight by 10% or more should lead to a dose re-calculation.

5.2.3 Nivolumab and/or ipilimumab cannot be dose reduced in response to toxicity, and can only be held or discontinued as per detailed algorithms for immune-therapy toxicity management below.

NCI CTCAE v 4 Grade	Nivolumab	Ipilimumab
0-1	No change from original starting dose	No change from original starting dose
2	Withhold drug, resume treatment when adverse reaction improves to grade 0 or 1	Withhold drug, resume treatment when adverse reaction improves to grade 0 or 1
3	Withhold drug, resume treatment when adverse reaction improves to grade 0 or 1 when given as a single agent	Withhold drug, resume treatment when adverse reaction improves to grade 0 or 1
Second episode of grade 3 or any episode of grade 4 toxicity	Permanently discontinue therapy and remove subject from trial	Permanently discontinue therapy and remove subject from trial

Certain adverse events that are possibly immune mediated warrant special monitoring and management, and are outlined below to guide investigators.

5.2.4.1 Pulmonary:

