Grade 2 AST or ALT > 3.0 to \leq 5 x ULN and/or total bilirubin > ULN to 1.5-to \leq 3 x ULN	
 Delay nivolumab or ipilimumab per protocol Increase frequency of monitoring to every 3 days 	
If returns to baseline:
 
 Resume routine monitoring, resume nivolumab or ipilimumab 
If persists > 5-7 days or worsens:
 
 0.5-1 mg/kg/day methylprednisolone or oral equivalent and when LFT returns to grade 1 or baseline, taper steroids over at least 1 month, consider prophylactic antibiotics for opportunistic infections, and resume nivolumab and ipilimumab
Grade 3 or 4 AST or ALT > 5 x ULN and/or total bilirubin > 3 x ULN	
 Discontinue nivolumab or ipilimumab* Increase frequency of monitoring to every 1-2 days 1.0 to 2.0 mg/kg/day methylprednisolone IV or IV equivalent* Add prophylactic antibiotics for opportunistic infection Consult gastroenterologist 	
If returns to grade 2:
 
 Taper steroids over at least one month 
If does not improve in > 3-5 days, worsens or rebounds:
 
 Add mycophenolate mofetil 1g twice daily If no response within an additional 3-5 days, consider other immunosuppressive agents per local guidelines

*The recommended starting dose for grade 4 hepatitis is 2 mg/kg/day methylprednisolone IV.

5.2.4.5 Neurological:

Rule out non-inflammatory causes. If non-inflammatory cause, treat accordingly and continue protocol therapy.

Grade of neurological toxicity (NCI CTCAE v 4)	Management	Follow-up
Grade 1 Asymptomatic or mild symptoms; intervention not indicated	
 Continue nivolumab or ipilimumab 	
 Continue to monitor the patient. 
If worsens:
 
 Treat as grade 2 or 3-4
Grade 2 Moderate symptoms; Limiting instrumental ADL	
 Delay nivolumab or ipilimumab Treat symptoms per institutional guidelines Consider 0.5-1mg/kg per day methylprednisolone IV or oral equivalent 	
If returns to baseline:
 
 Resume nivolumab or ipilimumab 
If worsens:
 
 Treat as Grade 3 - 4

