8.2 Adverse Event Reporting Requirements

Adverse event (AE) monitoring and reporting is a routine part of every clinical trial and is done to ensure the safety of subjects enrolled in the studies as well as those who will enroll in future studies using similar agents. Data on adverse events will be collected from the time of the initial study drug administration through 100 days after the last dose of study drug, that is nivolumab and/or ipilimumab. Any serious adverse event that occurs more than 100 days after the last study drug dose and is considered related to the study drug must also be reported. Serious Adverse Events (SAEs) will continue to be followed until:

- Resolution or the symptoms or signs that constitute the serious adverse event return to baseline;
- There is satisfactory explanation other than the study drug, nivolumab and/or ipilimumab, for the changes observed; or
- Death.

The investigator is responsible for the detection, documentation, grading and assignment of attribution of events meeting the criteria and definition of an AE or SAE. The definitions of AEs and SAEs are given below. It is the responsibility of the principal investigator to ensure that all staff involved in the trial is familiar with the content of this section.

Any medical condition or laboratory abnormality with an onset date before initial study treatment administration is considered to be pre-existing in nature. Any known pre-existing conditions that are ongoing at time of study entry should be considered medical history.

All events meeting the criteria and definition of an AE or SAE, as defined in Section 8.3, occurring from the initial study treatment administration through 100 days following the last dose of the study treatment must be recorded as an adverse event in the patient's source documents and on the CRF regardless of frequency, severity (grade) or assessed relationship to the study treatment.

In addition to new events, any increase in the frequency or severity (i.e., toxicity grade) of a pre-existing condition that occurs after the patient begins study treatment is also considered an adverse event.

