11.3 Data Analyses Plans

Primary Endpoint Analysis:

The primary endpoint for Cohort A and Cohort C is overall response rate using PSA criteria. The primary analysis will include the response count and proportion with the associated exact 95% binomial confidence interval in the mCRPC cohort. If stage 2 is initiated, then the efficacy analysis methods for the reported response confidence interval will be as described by Koyama and Chen [33].

Secondary Endpoint Analysis:

Efficacy in Cohort B will be described using overall response rate (CR/PR) using RECIST 1.1 criteria. The response count and proportion will be reported with the associated 95% exact binomial confidence interval.

Safety and tolerability of, nivolumab and ipilimumab combination therapy followed by nivolumab monotherapy, or nivolumab monotherapy only, will be described by the frequency and severity of adverse events by CTCAE criteria. The proportion of patients removed from treatment due to AEs will be reported. The number and proportion of patients with dose reductions and/or holds will be reported separately and overall. Each measure will be reported for the entire trial and separately by cohort.

Secondary efficacy time-to-event endpoints including radiographic progression-free survival (rPFS), progression-free survival (PFS), duration of response (DOR) among responders, duration of therapy (DOT), time to progression (TTP) and overall survival (OS) will be reported using Kaplan-Meier methods. The median, if reached, and the 52-week event-free proportion with the associated 95% greenwood formula confidence interval will be reported for each endpoint. For subjects with metastatic CRPC, PSA progression-free survival and time to PSA progression by PCWG3 criteria will also be described for Cohort A using the same the Kaplan-Meier measures described previously. Objective tumor response in patients with measurable disease by RECIST 1.1 criteria will be reported separately by location using PCWG3 recommendations and will include waterfall plots and counts with proportions and the associated 95% confidence intervals. Each endpoint will be reported for all patients if applicable and separately for each cohort.

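### Section 8.3 does not settle whether a new, asymptomatic, untreated laboratory abnormality that holds or ends study drug under 5.2 is recorded as an adverse event, so AE rates may be understated

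*Combined protocol and SAP*

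**What the plan says.** - **Section 8.3, general definition:** "An AE can be any unfavorable and unintended sign (including an abnormal laboratory finding".
- **Section 8.3, bullet beneath it:** "Abnormal laboratory values or test results constitute adverse events if they induce clinical signs or symptoms or require therapy". It continues: "They are to be captured under the signs, symptoms or diagnoses associated with them".
- **Section 8.2:** what goes on the case report form is "All events meeting the criteria and definition of an AE or SAE, as defined in Section 8.3", from first dose to 100 days after the last. A separate sentence also makes an increase in the frequency or toxicity grade of a pre-existing condition an AE.
- **Section 5.2, general table:** at grade 2, for either drug, "Withhold drug, resume treatment when adverse reaction improves to grade 0 or 1". Permanent discontinuation follows "Second episode of grade 3 or any episode of grade 4 toxicity". Neither row mentions symptoms or treatment.
- **Section 5.2.4.4, grade 2 liver tests:** delay drug and "Increase frequency of monitoring to every 3 days". Drug resumes once values are back at baseline. A steroid is listed only if the rise lasts beyond 5-7 days or worsens.
- **Sections 2.5.2 and 11.3:** AE frequency and severity by CTCAE 4.03 is a secondary endpoint. In 11.3, "The proportion of patients removed from treatment due to AEs will be reported", and dose holds are counted separately.

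**The concern.** The protocol acts on some findings by grade alone but may decline to record the same findings as AEs. If the 8.3 bullet is applied as a filter, a patient can have a dose held, or in a rarer case be taken off treatment, for a toxicity with no AE term and no grade in the database.

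The secondary safety endpoint is built from AE records. So is the AE material in the quarterly reports to the monitoring committee (section 12.0). Section 11.3 plans no separate tabulation of laboratory grades that would show what was left out. In a multi-center trial there is a second problem: sites that follow the general definition and sites that follow the bullet will record the same event differently, so part of any difference in AE rates could come from recording practice.

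**Working it through.** The plan states no AE rate or hold rate, so there is no figure to reproduce. The check compares the passages, then shows the arithmetic of one missed patient.

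**1. Does the bullet restrict?** The sentence before it already admits an abnormal laboratory finding without conditions. Unless the bullet narrows that, it adds no criterion. It then directs each qualifying abnormality to an associated sign, symptom or diagnosis, and an isolated asymptomatic value may have none. A restrictive reading is therefore natural, though the text does not force it.

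**2. Apply the restrictive reading to section 5.2.**

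| Row in 5.2 | Therapy listed at the outset? | Effect on drug | AE on the narrow reading? |
|---|---|---|---|
| Grade 2 liver tests, new onset (5.2.4.4) | No; steroid only on persistence or worsening | Delay, then resume | Not if asymptomatic and self-resolving |
| Grade 3-4 liver tests (5.2.4.4) | Yes, steroid | Discontinue | Yes |
| Grade 2-3 creatinine (5.2.4.7) | Yes, steroid | Delay | Yes |
| Grade 4 creatinine (5.2.4.7) | Yes, steroid | Discontinue | Yes |
| Grade 1 pneumonitis (5.2.4.1) | No drug therapy | Delay is only to be considered | Arguably yes: a named diagnosis |
| General table, grade 2 or first grade 3 | None listed | Withhold | Not if an untreated, asymptomatic laboratory value |
| General table, second grade 3 or any grade 4 | None listed | Permanent discontinuation | Not if an untreated, asymptomatic laboratory value |

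The gap is thus mainly the grade 2 liver-test row. Discontinuation without an AE record is reachable only through the general table.

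**3. Compare with the pre-existing-condition rule in 8.2.** Eligibility (3.1.12) admits AST and ALT up to 2.5 x ULN, within the grade 1 band of 5.2.4.4 (up to 3 x ULN). A patient who enters at grade 1 and reaches grade 2 has an AE under 8.2, with no symptom or therapy test. A patient who enters with normal values and reaches the same level, a larger change, may have none under the bullet.

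**4. Size per missed patient.** Inputs: planned N of 65, made up of 25 in Cohort A, 15 in B and 25 in C. If *k* patients have their only qualifying AE missed among *n*, the any-AE proportion falls by *k/n*.

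- Overall: 1/65 = 1.5 percentage points.
- Cohort A or C: 1/25 = 4.0 points.
- Cohort B: 1/15 = 6.7 points.
- Illustration, with *k* assumed to lie between 0 and 3 in a 25-patient cohort: 0 to 3/25 = 12 points.

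A patient with any other recorded AE does not move the any-AE proportion. The same step does apply to a single row of the AE table (one term at one grade) when the missed event is that patient's only one in the row. It also applies to the removal proportion when a removal is not attributed to an AE. On the narrow reading the error can only be downward.

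**The case against.** The strongest reply is that 8.3 does not exclude these events. The bullet says if, not only if, and follows a sentence that admits abnormal laboratory findings. Section 5.2 itself introduces its organ tables as adverse events and calls the trigger for a hold an adverse reaction, so many sites would record them. Section 8.2 captures worsening of a pre-existing abnormality. Section 11.3 counts holds whether or not an AE is linked, and scheduled blood results are still collected. A removed patient could still be logged under the unacceptable-AE reason in 5.4.

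Most of this stands, and it limits the point to an ambiguity. It does not remove it. The label in 5.2 sharpens the conflict with 8.3, which governs what is entered. A hold count supplies neither an AE term nor a grade. The pre-existing-condition route does not reach new-onset abnormalities.

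Some stronger inferences are tempting but not supported:

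- *Laboratory-driven discontinuations in general go unrecorded.* The liver-test and creatinine discontinuations in the organ tables list steroids from the outset, so they require therapy and are AEs on any reading.
- *Grade 1 pneumonitis is lost.* It is a diagnosis under which a scan finding can be captured, and 5.2.4.1 mandates no hold.
- *Prohibiting one growth-factor product in 5.3 means severe blood-count abnormalities are untreated and so unrecorded.* A ban on one product does not show that no therapy is required.
- *Each short liver-test rise costs a dose.* The table says delay and resume, so a brief rise may only shift a dose.

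**Conclusion.** The point holds as an unresolved conflict: within 8.3, and between 8.3 and the grade-based actions in 5.2. It bears mainly on new-onset, asymptomatic grade 2 liver-test rises that settle without treatment. Through the general table alone, it also bears on untreated grade 4 or second grade 3 laboratory values that end therapy. AE frequency and severity, and removals due to AEs, *may* be understated, and recording may differ by site.

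A reader might infer that the safety endpoint is certainly understated, or by a known number of patients. The documents do not support either: the wording leaves room for sites to record these events, and no incidence is given from which to count them. The per-patient steps of 1.5, 4.0 and 6.7 points rest on the planned cohort sizes and, for the any-AE rate, on the missed event being the patient's only qualifying AE. The correction is still worth making because any error runs one way and the remedy is a single sentence.

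**What to change.** Reconcile the two statements in 8.3 by extending the bullet. An abnormal laboratory value or test result should be recorded as an AE if it causes signs or symptoms, if it requires therapy, **or if it leads to a delay, hold or discontinuation of study drug under section 5.2**. It should be graded by CTCAE v4.03 and entered under the diagnosis where one exists, otherwise under the abnormality itself. Carry the same sentence into the case report form instructions so that all sites apply it. Each laboratory- or imaging-driven hold or removal in 11.3 will then have a matching graded AE.

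A further trigger for every grade 3 or higher abnormality, whatever its effect on dosing, is an optional addition. It does not follow from the contradiction.

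The cost is the amended wording, somewhat more AE entries and slightly higher reported AE rates. No test, visit, dosing rule or other clinical rule changes.

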8.4 Adverse Event Characteristics

8.4.1 CTCAE Term

(AE description) and grade: The descriptions and grading scales found in the NCI Common Terminology Criteria for Adverse Events (CTCAE) version 4.03 will be utilized for AE reporting. All appropriate treatment areas should have access to a copy of the CTCAE version 4.03. A copy of the CTCAE version 4.03 can be down loaded from the CTEP web site. (<http://ctep.cancer.gov>)

8.4.2 Attribution of the AE

The investigator or co-investigator is responsible for assignment of attribution.

Definite – The AE is *clearly related* to the study treatment.

Probable – The AE is *likely related* to the study treatment.

Possible – The AE *may be related* to the study treatment.

Unlikely – The AE is *doubtfully related* to the study treatment.

Unrelated – The AE is *clearly NOT related* to the study treatment.

8.5 Serious Adverse Event Reporting Guidelines

8.5.1 Reporting procedures for multi-site trials

All serious adverse events (SAEs) and unanticipated problems (UPs), regardless of causality to study drug, will be reported to the Principal Investigator and also to the Coordinating Center. All SAEs and UPs must be reported to the Coordinating Center within 24 hours of first awareness of the event. Events should be reported using the Coordinating Center SAE form as available in the study database. A copy of the Coordinating Center SAE form as available in the study database should be sent to the Coordinating Center via fax at [contact] or via email to [contact] within 24 hours of the site’s knowledge of the event.

Follow-up information must also be reported within 24 hours of receipt of the information by the investigator.

Participating sites should report all SAEs and UPs to their local IRB per current local institutional standards.

The Coordinating Center will disseminate information regarding SAEs and UPs to the participating sites within 5 days of review of the information by the Coordinating Center’s Principal Investigator (or designee in the event of extended absence) only in the case that the event(s) is believed to be related (i.e., possibly, probably, or definitely) to the study drug. The Coordinating Center will be responsible for reporting of events to the FDA and supporters, as appropriate (outlined below).

8.5.2 Reporting procedures to BMS

All Serious Adverse Events (SAEs) occurring from the initial study treatment administration through 100 days following the last dose of the study treatment will

be reported by the Coordinating Center to BMS Worldwide safety. Any SAEs occurring after 100 days following the last dose of the study treatment that are believed to be related to study drug will also be reported to BMS Worldwide safety.

The Coordinating Center will send the initial completed SAE Form within 24 hours of receipt via email to BMS Worldwide Safety ([contact]; [contact]).

If only limited information is initially available or an ongoing SAE changes in its intensity or relationship to the study drug, or if new information becomes available, a follow-up report will be generated and sent to BMS Worldwide Safety within 24 hours of receipt.

